Study protocol

Official Title of the study: Research on New Intelligent Diagnosis and Treatment Technologies for Early Lung Cancer Based on Multimodal Imaging Bronchoscopy Navigation

Affiliation: Sir Run Run Shaw Hospital, Zhejiang University School of MedicineDepartment: Department of Respiratory and Critical Care MedicineDate of the document: May 20, 2024

Research on new intelligent diagnosis and treatment technologies for early lung cancer based on multimodal imaging bronchoscopy navigation

Background

Lung cancer is one of the malignant tumors with the highest incidence and mortality rates worldwide. From the 1970s to the present, the mortality rate of lung cancer in China has been climbing year by year, and currently lung cancer ranks first in China in terms of incidence rate and mortality rate. Meanwhile, data show that 75% of lung cancer patients are already in advanced stage when they are diagnosed. The 5-year survival rate of advanced lung cancer in China is only 16.1%, while the 5-year survival rate of early lung cancer patients can reach 73%. Therefore, improving the early diagnosis rate of lung cancer will greatly reduce the mortality rate of lung cancer.

Regular chest computed tomography (CT) in the population can detect a large number of nodular lung lesions, and data show that lung nodules are detected in approximately 25% of the population on routine screening, most of which (96.4%) are benign. Further examination of these high-risk lung nodules is effective in improving early lung cancer detection and reducing mortality by approximately 20%. CT-guided percutaneous lung puncture is the mainstay of conventional diagnosis of lung nodules, and the risk of complications is a major concern. Its complications include pneumothorax, hemoptysis, and needle tract metastasis, among which the incidence of pneumothorax is 12.3% and hemoptysis is 20%. In recent years, the use of navigational tracheoscopy for peripheral lung nodule biopsy has gradually increased in the clinic due to good safety and accuracy. 2020 CHEST published a meta-analysis on navigational tracheoscopy, the incidence of pneumothorax is only 2%, which is obviously advantageous compared with the traditional methods.

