Inclusion criteria: (1) aged 18 years or above; (2) patients with one or more peripheral lung nodules suspected to be lung cancer or poorly absorbing lesions on conventional anti-infective therapy; (3) patients with nodule diameters \leq 30 mm (diameters mentioned in the text are the average of the maximum and minimum diameters; (4) the nodules were pure ground glass nodules, partially solid nodules, or solid nodules; (5) the nodule is surrounded by lung parenchyma and is not visible in the bronchial lumen above the segment.

Exclusion criteria: (1) preoperative judgment that it is difficult for the patient to benefit from bronchoscopic biopsy (e.g., high risk of bleeding due to perivascular encasement of the lesion, difficulty in reaching the airway adjacent to the lesion due to previous lung surgery, etc.); (2) those with incomplete clinical data; (3) those with missing visits after biopsy.

Interventions

After stratification according to the size of the lesion and the proportion of solid components in the lesion (\geq 50%, <50%), the eligible subjects were randomized into the new navigation system group (experimental group) and the old navigation system group (control group) in a 1:1 ratio. All included subjects underwent transnavigation-guided bronchoscopic lung biopsy at the respiratory endoscopy center. For pre-biopsy navigation path planning, the small airway reconstruction system-pro (SARS-pro) (self-developed by our team) was used in the experimental group and the conventional VBN system (LungPro; Bronchus Corporation) in the control group. The SARS-pro navigation system is an augmented reality optical navigation system based on VBN, which upgrades the small airway tree reconstruction navigation system through deep learning and multiple trainings.

Outcomes

The primary outcome was the diagnostic positive yield of the different navigation systems for PPL. The second outcome was the adverse events (hemoptysis, pneumothorax, and mediastinal emphysema) of the subjects.

Ethical approval and informed consent statement

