The trial was approved by the Ethics Committee of the Sir Run Run Shaw Hospital, Zhejiang University School of Medicine (approval number: 2024-1000) (See the attachment "Ethics Approval Document"). For statistical analysis, subject identities were expressed as codes, which did not involve disclosure of subjects' privacy and personal information, and the study did not involve commercial interests, so informed consent was waived by the Ethics Committee (See the attachment "Informed consent form").

Statistical analysis plan

Official Title of the study: Research on New Intelligent Diagnosis and Treatment Technologies for Early Lung Cancer Based on Multimodal Imaging Bronchoscopy Navigation

Date of the document: May 20, 2024

Research on New Intelligent Diagnosis and Treatment Technologies for Early Lung Cancer Based on Multimodal Imaging Bronchoscopy Navigation

Statistical analysis

For sample size calculation, a study reported a deep learning-based airway segmentation algorithm based on 40 CT images. Based on the benefit of a larger sample size in deep learning, the sample size in this study was set to 100. For subject characteristics, the quantitative data were tested for normality using the skewness and kurtosis methods, and the homogeneity of variance was tested using the Levene test. Normal distribution measurement data were described as mean and standard deviation [Mean (±SD)], and t test or t' test was utilized for comparison between groups. Nonnormal data were summarized as median and interquartile range [M (Q_1 , Q_3)], and group comparisons were made using the Wilcoxon rank sum test. Count data were reported as the number of cases and composition ratio [n (%)], and the chi-square test or the Fisher exact test was utilized for comparison between groups. Data cleaning was accomplished using Python 3.9.12 (Python Software Foundation, Delaware, USA), and the difference comparison was completed by R version 4.3.3 (R Foundation for Statistical Computing, Vienna, Austria). Statistical significance was set to P<0.05.

Data management and confidentiality

(1) The data is stored in the hospital's server with strict security protection and is not accessible to external networks; (2) All information related to the identity of the CT's patients is kept confidential, and the relevant information is not disclosed to the public outside of the scope permitted by relevant laws and/or regulations.

Ethics Committee Approval (Original Chinese version)

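### The safety outcome names three events, with no category for other serious events and no grading of bleeding, so the per-arm safety comparison can be incomplete

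*Combined protocol and SAP*

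**What the plan says.** The Outcomes section of the protocol makes safety the only secondary outcome: "The second outcome was the adverse events (hemoptysis, pneumothorax, and mediastinal emphysema) of the subjects". The brackets contain no *e.g.*, *including* or *etc.* Nothing else in the protocol or SAP text widens or defines the list. It gives no definition or grade of hemoptysis, no serious-event category, no collection window and no reporting procedure.

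Three other places bear on the point:

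- **Inclusion and exclusion criteria.** Exclusion (1) gives, as one example of a patient unlikely to benefit from biopsy, "high risk of bleeding due to perivascular encasement of the lesion". Exclusion (3) removes "those with missing visits after biopsy".
- **Background.** For CT-guided percutaneous puncture the protocol writes "Its complications include pneumothorax, hemoptysis, and needle tract metastasis, among which the incidence of pneumothorax is 12.3% and hemoptysis is 20"%. For navigational bronchoscopy it gives one complication rate: "the incidence of pneumothorax is only 2"%.
- **SAP, Statistical analysis.** The plan states that "the sample size in this study was set to 100" and that "Statistical significance was set to P<0.05". Count data are covered by "the chi-square test or the Fisher exact test was utilized for comparison between groups", in a run of text introduced as describing subject characteristics. The SAP does not mention adverse events.

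**The concern.** A safety outcome has to be able to show harm if harm occurs. Three features of this one work against that.

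First, no category is provided for serious events other than the three named, so a death or unplanned admission from another cause has no row in the planned result. Second, bleeding enters through one undefined, ungraded term. Bleeding seen or controlled through the bronchoscope, or bleeding that ends the procedure early, may or may not be recorded, depending on how an operator reads the word. Where it is recorded, a trivial and an important bleed carry equal weight. Third, exclusion (3) operates after the biopsy. A patient who fails to return because of a serious event is removed together with that event.

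At stake is whether similar adverse-event counts in the two arms can be read as similar safety. The primary outcome, diagnostic yield, is not affected by the definition of the safety outcome.

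**Working it through.** The plan gives no target rate, power or expected event count for safety, so there is no stated figure to reproduce. The check has two parts.

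**1. What the text provides for each kind of event**

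| Event in a biopsied patient | Place in the stated outcome | Consequence |
|---|---|---|
| Pneumothorax or mediastinal emphysema, visits complete | Named | Counted |
| Trace of blood coughed up | Hemoptysis | Counted as one event |
| Hemoptysis needing intervention | Hemoptysis | Counted as one event, not distinguished from the row above |
| Bleeding seen or controlled during the procedure, nothing coughed up | Not stated; depends on how hemoptysis is read | May or may not be counted |
| Death, unplanned admission or other serious event outside the three | None | Need not be counted |
| Any event, later visits missing | Patient removed by exclusion (3) | Can be lost |

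On whether the list is meant to be complete: exclusion (1), in the same part of the protocol, carries both *e.g.* and *etc.*, so the authors mark a list as open when they intend it. The safety list has no such mark. This supports the closed reading but does not prove it.

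**2. What about 50 per arm can say about safety**

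Inputs: total 100 (SAP, Statistical analysis); 1:1 allocation (Interventions), hence n = 100/2 = 50 per arm; alpha 0.05, taken as two-sided for the power figures because the SAP does not state sidedness. I take 100 to be the number of randomised patients. The SAP's justification, which rests on a study of 40 CT images, leaves that unstated.

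*Zero events.* The one-sided 95% upper bound on the true rate is 1 − 0.05^(1/n).
- n = 50: 1 − 0.05^(1/50) = 5.8%
- n = 100: 1 − 0.05^(1/100) = 3.0%

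*Chance of seeing at least one event in an arm.* This is 1 − (1 − p)^50. Only the 2% has a source (the Background's pneumothorax figure); the other rates are assumptions.
- p = 1%: 39%
- p = 2%: 64%
- p = 5%: 92%

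*Power to detect a doubling.* Normal approximation, n = 50 per arm: Φ{[|p₂ − p₁|√n − 1.96√(2p̄(1 − p̄))] / √(p₁(1 − p₁) + p₂(1 − p₂))}, where p̄ is the mean of the two rates. All rates are assumptions; 20% happens to equal the Background's percutaneous hemoptysis figure.
- 5% v 10%: [0.05 × 7.071 − 1.96 × 0.3725]/0.3708 = −1.015, power 16%
- 10% v 20%: [0.10 × 7.071 − 1.96 × 0.5050]/0.5000 = −0.565, power 29%
- 20% v 40%: [0.20 × 7.071 − 1.96 × 0.6481]/0.6325 = 0.228, power 59%

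A non-significant comparison would therefore be the usual result even where one arm had twice the event rate. The trial can describe safety but cannot establish that it is equal, and it can say nothing about event types it does not record.

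**The case against.** **The list may not be closed.** The protocol never says *only*, and the brackets could name just the main expected events. Hemoptysis is undefined, and the Background uses it as its sole bleeding term for percutaneous biopsy, so the authors may mean it as a general word for biopsy bleeding. This stands. A reader might infer that procedural bleeding is excluded from the outcome; the text shows only that it is not provided for. The ambiguity still has to be removed, because classification could differ between operators.

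**Screening out a risk is not a contradiction.** A reader might infer that exclusion (1) conflicts with the outcome list, since it mentions bleeding and the list has no separate bleeding endpoint. The documents do not support that. The criterion gives high bleeding risk as one example of a patient unlikely to benefit, and keeping such lesions out is compatible with any outcome list.

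**No mechanism is documented.** The arms differ in pre-biopsy path planning. No passage links planning through small airways to bleeding, and no bronchoscopic bleeding rate is given. This also stands. The point rests on what is recorded, not on an expected difference between the systems.

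**Better recording will not rescue power.** True, as the figures above show. That argues for descriptive reporting; it does not justify leaving events unrecorded.

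**Safety is secondary.** Also true, and it limits the severity. It is nonetheless the only secondary outcome.

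**Conclusion.** The concern holds in a limited form. As written, serious events outside the three named items need not enter the per-arm safety result, bleeding is neither defined nor graded, and biopsied patients with missing visits can take their events out of the count. The comparison can therefore be incomplete.

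A reader might go further and infer that the trial's safety conclusion will be wrong, or that important bleeding will differ between arms unseen. The documents do not support either inference. They state no safety or equivalence hypothesis and supply no rate from which to estimate how many events would be missed. The size of the gap is unknown; the figures above bound only what 50 per arm could show if events were fully recorded.

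The conclusion assumes that the bracketed list is the whole safety outcome, that exclusion (3) is applied to patients already randomised and biopsied, and that the attached ethics and consent pages, which were not available for checking, add no safety definition. The change should be made because it is cheap and specific. It does not call the primary analysis into question.

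**What to change.** In Outcomes, restate the safety outcome as:

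1. bleeding during or after biopsy, in place of hemoptysis, shown separately as (a) bleeding with no intervention and (b) bleeding needing any intervention or early termination of the procedure;
2. pneumothorax;
3. mediastinal emphysema;
4. any other serious event, including death and unplanned admission, from biopsy to the post-biopsy visit. State when that visit falls, since the protocol gives no timing.

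In the SAP, add that each item is reported as a count and percentage per arm for every randomised patient who was biopsied, including those with missing later visits, and give the number without a post-biopsy visit in each arm. Present the results descriptively. State that a non-significant difference with about 50 per arm is not evidence of equal safety.

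This alters what is counted, not how patients are managed. The cost is a few extra record fields, some additional abstraction and one table. The downside for the sponsor is an event count that will look less favourable than the three-item list would give.

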To improve the diagnostic rate of lung nodules by navigational bronchoscopy, this project has conducted a preliminary exploration to address the three main issues mentioned above. The preliminary research found that the mainstream whole-lung navigation systems on the market, including The SPiN Thoracic Navigation System magnetic navigation system from Veran, the virtual bronchoscopic navigation (VBN) System from Lungpro of Broncus, and the Super Dimension Electromagnetic Navigation System from Medtronic, are all similar, although there are differences in the operation process. Despite the differences in operation procedures, the core technology of computerized virtual bronchial tree imaging is similar, and all of them are suboptimal for the reconstruction of small airways less than 3 mm. The main reason is that for small airways less than 3 mm, the airway features are not obvious or missing, which are difficult to be extracted by the existing navigation algorithms. To address this problem, on the basis of the existing algorithms to recognize airway segments, deep learning technology is added to do super-resolution reconstruction of the original CT by super-

resolution convolutional neural network (SRCNN), so as to enhance the visual features of the airway smaller than 3mm, and link the 3D-VNET network model with its own attention mechanism to intelligently recognize more small airway segments smaller than 3mm.

Study purpose and design

To improve the problems of recognition, extraction, and three-dimensional reconstruction of 2-3mm small airways that have not been solved by mainstream navigation software on the market through deep learning methods based on the VBN navigation system, and evaluate the accuracy of the improved navigation system and the original navigation system in the diagnosis of peripheral pulmonary lesions (PPL) through a randomized controlled trial.

Study population

Subjects for this single-center randomized controlled trial were recruited from August 2023 to December 2024 at the Sir Run Run Shaw Hospital, Zhejiang University School of Medicine.

Inclusion and exclusion criteria

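### The stated grounds for waiving informed consent, coded identities and no commercial interest, do not cover random allocation to a self-developed navigation system for an invasive biopsy

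*Combined protocol and SAP*

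**What the plan says.** The protocol's section on ethical approval and informed consent gives two grounds for the waiver. The first is privacy: "For statistical analysis, subject identities were expressed as codes". The second is financial, and the waiver follows from it directly: "the study did not involve commercial interests, so informed consent was waived by the Ethics Committee". The section refers to two attachments, an ethics approval document and a document titled as a consent form. Neither is in the text available for this review.

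The design is set out elsewhere in the protocol. Study purpose and design says the two systems are to be compared "in the diagnosis of peripheral pulmonary lesions (PPL) through a randomized controlled trial". Under Interventions, "the eligible subjects were randomized into the new navigation system group (experimental group) and the old navigation system group (control group", in a 1:1 ratio. The same section says "All included subjects underwent transnavigation-guided bronchoscopic lung biopsy at the respiratory endoscopy center" and, for path planning, "the small airway reconstruction system-pro (SARS-pro) (self-developed by our team) was used in the experimental group", with the marketed LungPro system as control. Under Outcomes, "The second outcome was the adverse events (hemoptysis, pneumothorax, and mediastinal emphysema) of the subjects".

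**The concern.** A waiver has to rest on reasons that address what is done to the people concerned. Coded data and the absence of a commercial interest are reasons one would expect for a review of existing records, where nothing is done to the patient. Here the trial assigns an intervention. Chance, rather than the treating physician or the patient, decides which software plans the route for an invasive biopsy, and one of the two is a new system built by the investigating team. Coding the data afterwards cannot justify assigning patients beforehand.

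Two things are at stake. One is patient protection: the protocol gives no basis for allocating subjects to the new system without asking them. The other is the data: if the recorded basis for enrolment does not fit the design, the committee or a later reader may question whether the randomised subjects' data can be used.

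**Working it through.** The plan states no figure on this point, so there is nothing to reproduce. The check sets each stated ground against each feature of the design.

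1. **Random allocation (Interventions).** Coding identities for analysis operates after allocation and does not address it. Absence of commercial interest does not address it either.
2. **Use of a self-developed system in one arm (Interventions).** Coding is irrelevant to it. Absence of commercial interest says something about the team's motive and nothing about the patient's agreement to be assigned the system.
3. **Physical risk of the procedure (Interventions, Outcomes).** Neither ground mentions it, although haemoptysis, pneumothorax and mediastinal emphysema are collected as the second outcome.
4. **Any other ground.** The available text supplies none, and it describes no separate consent to the biopsy or to the allocation.

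**Scale of procedural risk, for illustration only.** Inputs: a pneumothorax rate of 2% for navigational bronchoscopy (Background) and a sample size of 100 (SAP, Statistical analysis), taken here as 100 trial subjects split 1:1.
- Expected cases: 100 × 0.02 = 2 overall; 50 × 0.02 = 1 per arm.
- Chance of at least one case: 1 − 0.98^100 = 0.867 overall; 1 − 0.98^50 = 0.636 in one arm.

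These figures show that the procedure carries physical risk. They do not measure risk added by trial entry or by SARS-pro, because both arms have the procedure and the rate is not specific to either system.

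**Timing.** Study population gives recruitment from August 2023 to December 2024, which is 5 + 12 = 17 calendar months. The document is dated May 20, 2024. August 2023 to April 2024 is 9 full months, so at least 9/17 = 53% of the window had passed if recruitment opened at the start of August. With even accrual, which is an assumption, about half or slightly more of the subjects would already have been enrolled by the document date. Any change therefore has to treat subjects already enrolled separately from those still to come.

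**The case against.** The strongest reply is that much of the relevant material is out of sight. The two attachments and the consent pages are not available, so the committee's full reasoning, or a clinical consent to bronchoscopy, may be there. This stands, and it limits the point to the basis that the protocol itself states. It does not remove the point: the sentence giving the reasons is legible and complete, and those reasons do not fit the design. Routine consent to a procedure would also not by itself cover random assignment to a team-developed system.

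A second reply is that every subject has a navigation-guided biopsy, so the trial changes only the planning software. That is correct, and it is why the gap concerns allocation and use of the new system rather than the biopsy as such. The protocol nonetheless treats safety as a question by making adverse events an outcome.

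A third reply is that the committee approved the waiver. Approval does not make the recorded reasoning fit the design, and the remedy goes back to the same committee.

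A reader might also take this for a records study, given the past tense and the exclusions for incomplete clinical data and missed visits after biopsy. The waiver grounds would then make sense, but the description as a randomised trial would not. The protocol says randomised in more than one section.

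Four stronger readings are tempting, and the documents do not support them:
- That patients were told nothing of the allocation, the system or the risks. The text says consent was waived; it does not say what was disclosed.
- That the section contradicts itself by citing a consent form while waiving consent. The attachment's content is unseen, and it may be the waiver document filed under that name.
- That subjects not asked about trial entry bear two extra pneumothoraces. The 2% rate applies to the procedure in both arms.
- That 100 is settled as the number of trial subjects. The SAP justifies it by a 40-image segmentation study and by the benefit of larger samples in deep learning, so what it counts is unclear.

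**Conclusion.** The point holds in a limited form. The two grounds stated for the waiver do not cover prospective 1:1 randomisation to a self-developed or a marketed planning system for an invasive biopsy. This is a stated rule that does not fit the stated design, and not simply a missing detail. It reaches every randomised subject for the waiver of consent to allocation, and the experimental arm for use of the new system. The conclusion depends on no sample size or event rate.

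It rests on two premises: that the trial is prospective and randomised as the protocol says, and that the ethics statement gives the operative reasons. It does not establish that the committee lacked another basis, that no patient consented to the procedure, or that SARS-pro adds risk. Because it concerns patient protection and the usability of the data, it should be settled before further subjects are randomised.

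**What to change.** - **Subjects not yet randomised.** Replace the waiver with prospective consent taken before randomisation. It should name the random allocation, the self-developed status of SARS-pro and the three listed adverse events.
- **Ethics statement.** Remove coded data and absence of commercial interest as the basis for a waiver.
- **Subjects already enrolled.** Ask the Ethics Committee to rule on whether they must be notified and whether their data may be used, and record the ruling in the protocol. If recruitment has closed, this is the part that remains.
- **Clarification.** State what consent, if any, was taken for the biopsy and for the allocation, and what the attachment titled as a consent form is.

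The cost is an ethics amendment, a consent step before randomisation and some refusals. The planned tests need not change, but the analysed sample may if the committee excludes earlier subjects. In that case the SAP should say how the exclusion is handled and reported by arm.

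### The sample size of 100 rests on a deep-learning argument that cannot size the randomised comparison of diagnostic yield, and no confidence interval for the yield difference is planned

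*Combined protocol and SAP*

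**What the plan says.** The protocol's statement of purpose has two parts: improve small-airway reconstruction by deep learning, then compare the improved and original navigation systems in a randomised trial. Under Interventions, eligible subjects are "randomized into the new navigation system group (experimental group) and the old navigation system group (control group) in a 1:1 ratio". Under Outcomes, "The primary outcome was the diagnostic positive yield of the different navigation systems for PPL".

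The SAP (Statistical analysis) introduces its sample size by noting that "a study reported a deep learning-based airway segmentation algorithm based on 40 CT images", and continues: "Based on the benefit of a larger sample size in deep learning, the sample size in this study was set to 100". It gives no expected yield in either arm, no difference to detect, no power, no precision target and no allowance for losses.

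The same paragraph then turns to subject characteristics and lists methods by data type. Count data are summarised as number and percentage, and "the chi-square test or the Fisher exact test was utilized for comparison between groups". "Statistical significance was set to P<0.05"; sidedness is not given. No sentence assigns a test to the primary outcome, and no confidence interval for a between-group difference is mentioned.

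**The concern.** The number of images that helps an algorithm learn airway structure has no bearing on how many patients are needed to compare two proportions. The stated rationale may serve the first aim. For the second, which carries the primary outcome, there is none.

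The number is also not fully defined. Subjects are randomised, so 100 subjects in total is the natural reading. But the precedent is counted in CT images, the inclusion criteria admit "patients with one or more peripheral lung nodules", and the exclusion criteria remove people with incomplete data or missed visits after biopsy. The text does not say whether 100 is a total or per arm, or whether it is before or after such losses.

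What is at stake is how a non-significant result is read. If only percentages and a P value are reported, and the trial's power for moderate gains is low, P above 0.05 invites the conclusion that the two systems perform equally. The data may be compatible with a sizeable gain.

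**Working it through.** **Can 100 be reproduced?** No. A two-proportion calculation needs two yields, a significance level and a power. The SAP supplies only the 5% level, and a count of 40 CT images is not an input to any such formula. The useful check is therefore what 100 could show.

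**Inputs**
- Size: 100 subjects in total, 50 per arm (SAP; 1:1 from Interventions), all evaluable. This is the natural reading, not a stated one.
- Control yield: 80%, the overall rate for navigation bronchoscopy in the protocol's Background. The SAP does not use it. Control yields of 70% and 60% are assumptions for sensitivity.
- Level: 5%, taken as two-sided (assumption).
- Gain: 10 points (assumption; the documents give no target).

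**Power.** For n per arm and yields p1 and p2, exact power is the sum, over all pairs (i, j) from 0 to n, of Bin(i; n, p1) × Bin(j; n, p2) for tables where the test rejects. With n = 50:

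| Control vs experimental | Uncorrected chi-square | Fisher |
|---|---|---|
| 80% vs 90% | 30.3% | 19.5% |
| 70% vs 80% | 21.2% | 15.5% |
| 60% vs 70% | 18.0% | 13.2% |
| 80% vs 95% | 66.4% | 50.8% |

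**Experimental yield needed for 80% power, n = 50**

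| Control | Uncorrected chi-square | Fisher |
|---|---|---|
| 80% | 96.7% | 98.2% |
| 70% | 91.2% | 92.8% |
| 60% | 84.5% | 86.0% |

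**Precision.** Wald 95% half-width = 1.96 × √[p1(1−p1)/n + p2(1−p2)/n], with n = 50.
- 80% in both arms: 1.96 × √(0.16/50 + 0.16/50) = 15.7 points. For 70% and 60% in both arms: 18.0 and 19.2 points.
- At the chi-square thresholds above (control 80%, 70%, 60%): 12.1, 14.9 and 16.9 points.

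**A worked result.** Suppose 40/50 in control and 45/50 in the experimental arm.
- Pooled proportion = 85/100 = 0.85, so chi-square = 0.10² / (0.85 × 0.15 × 2/50) = 0.01/0.0051 = 1.96, P = 0.16. Fisher gives P = 0.26.
- The difference is 10 points. The Wald 95% CI is 10 ± 13.9, or −3.9 to 23.9; the Newcombe score interval is −4.3 to 24.2.

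The P value alone would be reported as no significant difference. The interval shows that the data allow anything from a small loss to a gain of about 24 points.

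**Sensitivity to the reading of 100.** If 100 is per arm, power for 80% vs 90% is 51.8% (uncorrected chi-square) or 44.4% (Fisher). With control at 80%, 80% power needs about 93% to 94%. If 100 is randomised in total and an assumed 10% are lost (45 per arm), power for 80% vs 90% is 27.7% or 17.9%. No reading supplies the missing link between the deep-learning rationale and the yield comparison.

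**The case against.** The strongest objection is that nothing here shows 100 to be inadequate. This stands. A reader might infer that the trial is underpowered, but the documents state no difference the trial is meant to detect. 100 in total would serve a gain of about 17 points from 80%, and the 10-point gain used above is an assumption. Sidedness is also unstated: a one-sided 5% test would raise power for 80% vs 90% to about 40% (normal approximation).

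Second, a reader might infer that the SAP assigns chi-square or Fisher to diagnostic yield. It does not say so, because the methods follow an opening about subject characteristics. Applying the count-data sentence to yield is a reasonable reading, but only a reading. On the stricter one no primary analysis is named, which widens the gap.

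Third, a reader might infer that 100 is a number of scans and that the randomised trial has no stated size. The text does not support going that far: the protocol speaks of randomised subjects, and the SAP of the sample size of the study. The request is for one clarifying phrase.

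Finally, anyone can compute the interval from the counts and percentages. That is true, so the missing CI is the smaller part of the point. The SAP still does not plan the interval or base its conclusion on it.

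**Conclusion.** The point holds in this form: the stated basis for 100 cannot justify the size of the randomised yield comparison, and the plan, on the generous reading of its count-data methods, includes no interval for the difference. It should be fixed. Confidence in the mismatch is high because it rests on the text alone.

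The size of the consequence is conditional on 50 evaluable subjects per arm, a two-sided 5% level and assumed yields. On that footing, power for a 10-point gain is about 30% or less at control yields of 60% to 80%, and only large gains are detectable with 80% power. The finding concerns the justification and what a result can support. It does not say that the trial should have been larger.

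**What to change.** 1. Remove the deep-learning rationale as the basis for the randomised comparison. If a number of CT scans applies to the algorithm work, give it separately.
2. State that 100 is subjects in total, or what else it counts, and whether it means randomised or evaluable. State the true basis, for example feasibility. If it was not a power calculation, say so and add:

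> With 50 evaluable patients per arm and a two-sided 5% level, 80% power requires an experimental yield of about 97%, 91% or 85% (uncorrected chi-square) or 98%, 93% or 86% (Fisher) for assumed control yields of 80%, 70% or 60%. The Wald 95% CI half-width for the difference is about 12 to 17 points at those yields and 16 to 19 points if yields are equal.

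   Recalculate if 100 is per arm or before losses. If it counts nodules, give the number of patients too and allow for unequal numbers of nodules per patient.
3. Name the test for the primary outcome and add:

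> The primary result will be the difference in yield with its 95% CI (Newcombe score method) beside the test. A non-significant result will not be interpreted as equal yield.

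4. Give the change its actual date and state whether results by arm were known when it was made. The protocol puts recruitment at August 2023 to December 2024, and the SAP is dated May 20, 2024.

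The cost is SAP wording, one confidence interval and a less favourable statement of what the trial can show. No patients are added. The change does not raise power; it makes clear what a result can support.
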